APPENDIX B: INTERNATIONAL PROGNOSTIC SCORING SYSTEM SCORE – REVISED

IPSS-R Cytogenetic Risk Groups*, **

Cytogenetic Prognostic Subgroups	Cytogenetic Abnormalities
Very good	-Y, del(11q)
Good	Normal, del(5q), del(12p), del(20q), double including del(5q)
Intermediate	del(7q), +8, +19, i(17q), any other single or double independent clones
Poor	-7, inv(3)/t(3q)/del(3q), double including -7/del(7q), Complex: 3 abnormalities
Very poor	Complex: >3 abnormalities

IPSS-R Prognostic Score Values*

Prognostic Variable	0	0.5	1	1.5	2	3	4
Cytogenetics	Very Good	-	Good	-	Intermediate	Poor	Very Poor
BM Blasts (%)	≤2	-	>2 - <5	-	5 - 10	>10	-
Hemoglobin (g/dL)	≥10	-	8 - <10	<8	-	-	-
Platelets (x 10 ⁹ /L)	≥100	50 - <100	<50	-	-	-	-
ANC (x 10 ⁹ /L)	≥0.8	<0.8	-	-	-	-	-

IPSS-R Prognostic Risk Categories/Scores*

Risk Category	Risk Score
Very Low	≤1.5
Low	>1.5 - 3
Intermediate	>3 - 4.5
High	>4.5 - 6
Very High	>6

IPSS-R: Prognostic Risk Category Clinical Outcomes*

	No. pts	Very Low	Low	Intermediate	High	Very High
Subjects (%)	7012	19%	38%	20%	13%	10%
Survival***	-	8.8	5.3	3.0	1.6	0.8
AML/25%***,^	-	NR	10.8	3.2	1.4	0.7

^{*} Greenberg et al. 2012. ** Schanz et al. 2012.

APPENDIX C: DIAGNOSIS OF IDIOPATHIC/DE NOVO MDS ACCORDING TO WORLD HEALTH ORGANIZATION

Name	Dysplastic Lineages	Cytopenias*	Ring Sideroblasts as % of Marrow Erythroid Elements	BM and PM Blasts	Cytogenetics by Conventional Karyotype Analysis
MDS with single lineage dysplasia (MDS-SLD)	1	1 or 2	< 15% / < 5% [†]	BM < 5%, PB < 1%, no Auer rods	Any, unless fulfills all criteria for MDS with isolated del(5q)
MDS with multilineage dysplasia (MDS- MLD)	2 or 3	1-3	< 15% / < 5% [†]	BM < 5%, PB < 1%, no Auer rods	Any, unless fulfills all criteria for MDS with isolated del(5q)
MDS with ring sidero	blasts (MDS-R	S)			
MDS-RS with single lineage dysplasia (MDS- RS-SLD)	1	1 or 2	≥ 15% / ≥ 5% [†]	BM < 5%, PB < 1%, no Auer rods	Any, unless fulfills all criteria for MDS with isolated del(5q)
MDS-RS with multilineage dysplasia (MDS- RS-MLD)	2 or 3	1-3	≥ 15% / ≥ 5% [†]	BM < 5%, PB < 1%, no Auer rods	Any, unless fulfills all criteria for MDS with isolated del(5q)
MDS with isolated del(5q)	1-3	1-2	None or any	BM < 5%, PB < 1%, no Auer rods	del(5q) alone or with 1 additional abnormality except -7 or del (7q)
MDS with excess blas	ts (MDS-EB)		•		T (D)
MDS-EB-1	0-3	1-3	None or any	BM 5%-9% or PB 2%- 4%, no Auer rods	Any
MDS-EB-2	0-3	1-3	None or any	BM 10%-19% or PB 5%-19%, no Auer rods	Any
MDS, unclassifiable (MDS-U)				
with 1% blood blasts	1-3	1-3	None or any	BM < 5%, PB = $1\%^{\ddagger}$, no Auer rods	Any
with single lineage dysplasia and pancytopenia	1	3	None or any	BM < 5%, PB < 1%, no Auer rods	Any
based on defining cytogenetic abnormality	0	1-3	< 15% §	BM < 5%, PB < 1%, no Auer rods	MDS-defining abnormality
Refractory cytopenia of childhood	1-3	1-3	None	BM < 5%, PB < 2%	Any

^{*} Cytopenias defined as: hemoglobin, < 10 g/dL; platelet count, $< 100 \times 10^9 \text{/L}$; and absolute neutrophil count, $< 1.8 \times 10^9 \text{/L}$. Rarely, MDS may present with mild anemia or thrombocytopenia above these levels. PB monocytes must be $< 1 \times 10^9 \text{/L}$.

Abbreviations: BM = bone marrow; MDS = Myelodysplastic Syndrome; PB = peripheral blood.

Adapted from Arber et al. 2016.

73 of 77

Version 3.0; 31 July 2023

[†] If SF3B1 mutation is present.

[‡] One percent PB blasts must be recorded on at least 2 separate occasions.

[§] Cases with ≥ 15% ring sideroblasts by definition have significant erythroid dysplasia, and are classified as MDS-RS-SLD.

APPENDIX D: ECOG PERFORMANCE STATUS

Grade	ECOG Performance Status
0	Fully active, able to carry on all pre-disease performance without restriction
1	Restricted in physically strenuous activity but ambulatory and able to carry out work of a light or sedentary nature, eg, light housework, office work
2	Ambulatory and capable of all self-care but unable to carry out any work activities; up and about more than 50% of waking hours
3	Capable of only limited self-care; confined to bed or chair more than 50% of waking hours
4	Completely disabled; cannot carry on any self-care; totally confined to bed or chair
5	Dead

Source: Oken et al. 1982.

APPENDIX E: CLINICAL LABORATORY ANALYSES

Chemistry

Alanine aminotransferase Ferritin, transferrin (TIBC) and iron level

(timing per Table 1-1, and Table 1-2)

Albumin Gamma-glutamyl transferase

Alkaline phosphatase Glucose

Amylase Lactate dehydrogenase

Aspartate aminotransferase Lipase
Bicarbonate Magnesium
Bilirubin – total, direct, indirect Phosphorus
Blood urea nitrogen Potassium
Calcium Sodium
Chloride Total protein
Creatinine Uric acid

Erythropoietin (Screening only)

Hematology

Hematocrit White blood cell (WBC) count and differential:

Hemoglobin • Basophils

Red blood cell (RBC) count • Eosinophils

Reticulocyte count (% and absolute) • Lymphocytes

Mean corpuscular hemoglobin concentration

• Monocytes

(MCHC)

• Neutrophils

Mean corpuscular volume (MCV)

• Blasts

RBC distribution width (RDW)

Absolute neutrophil count (ANC)

Platelets

Hemoglobin Electrophoresis

Screening only

Coagulation

International normalized ratio (INR)

Partial thromboplastin time (PTT)

Prothrombin time (PT) Fibrinogen

Serology

Hepatitis B surface antigen (HepBsAg)

Hepatitis C virus (HCV) by polymerase chain reaction (PCR)

Hepatitis B core antibody (HepBcAb) Human immunodeficiency virus (HIV)

Urinalysis

Bilirubin Blood
Glucose Ketones
Leukocyte esterase pH

Nitrite Specific gravity

Protein Urobilinogen

Microscopic analysis (RBCs, WBCs, microalbumin, bacteria, crystals, and casts) will be performed locally as

clinically indicated.

Pregnancy Tests (Female patients)

Serum (Screening) Urine (post-Screening)

APPENDIX F: EXAMPLES OF DRUGS THAT ARE STRONG INDUCERS OF CYP3A4/5

Strong Inducers:

Apalutamide, carbamazepine, enzalutamide, mitotane, phenytoin, rifampin, St. John's wort

Additional information can be found at:

https://www.fda.gov/drugs/drug-interactions-labeling/drug-development-and-drug-interactions-table-substrates-inhibitors-and-inducers#table3-3

APPENDIX G:	SAMPLE TRANSFUSIO	ON PLAN: LTB AND HTB PATIENTS
Patient:		
Date of plan:		
Planned frequency	y of transfusions:	
Patient will	receive transfusions approxin	nately every weeks
Baseline pre-trans	sfusion Hb threshold	
	level above, a transfusion is retreatment mean of Hb.	equired. Threshold should be determined based on
pre-transfusion Hb	threshold for that patient, trans	is increased by ≥ 1 g/dL compared to the asfusion may be delayed by a minimum of 7 days duced by 1 or more RBC units.
Pre-treatment Hb	results from ≥ 16 weeks pri	or to start of study treatment:
Date		Hb Result

4.2.1.	Analysis of Primary Endpoints	20
4.2.2.	Analysis of Secondary Endpoints	21
4.3.	Pharmacokinetic Evaluations	21
4.4.	Safety Analyses	21
4.4.1.	Study Drug Exposure	21
4.4.2.	Adverse Events	22
4.4.3.	Laboratory Data	23
4.4.4.	Vital Signs and Physical Examination	24
4.4.5.	Cardiac Monitoring	24
5.	Changes from protocol	25
5.1.	Endpoint Phrasing Clarifications	25
5.2.	Changes to Planned Analyses	25
5.3.	Additional Changes	26
6.	References	27

LIST OF ABBREVIATIONS AND DEFINITION OF TERMS

Abbreviation	Definition
2,3-DPG	2,3-diphosphoglycerate
AE	Adverse event
ALP	Alkaline phosphatase
ALT	Alanine aminotransferase
AST	Aspartate aminotransferase
ARC	Absolute reticulocyte count
ATC	Anatomical Therapeutic Chemical
ATP	Adenosine triphosphate
BMI	Body Mass Index
BP	Blood pressure
CI	Confidence interval
CNS	Central nervous system
CRF	Case report form
CS	Clinically Significant
CSR	Clinical study report
CTCAE	Common Terminology Criteria for Adverse Events
DBL	Database lock
DLT	Dose-limiting toxicity
ECG	Electrocardiogram
EES	Efficacy Evaluable Set
EOET	End of Extended Treatment
EOPT	End of Primary Treatment
EOS	End of Study
FAS	Full Analysis Set
FCR	Fraction of cells remaining
FDA	Food and Drug Administration
Hb	Hemoglobin
HI-E	Hematologic Improvement - Erythroid
HTB	High transfusion burden
ICH	International Conference on Harmonization
ICT	Iron chelation therapy
IEC	Independent Ethics Committee
IPSS-R	Revised International Prognostic Scoring System
ITT	Intent-to-treat
IWG	International Working Group
LDH	Lactate dehydrogenase
LIC	Liver Iron Concentration
LS	Least squares

Abbreviation	Definition
LTB	Low transfusion burden
m ²	Square meter
MCHC	Mean corpuscular hemoglobin concentration
MedDRA	Medical Dictionary for Regulatory Activities
MDS	Myelodysplastic syndrome
MMRM	Mixed model repeated measures
Msec	Millisecond
NCS	Not clinically significant
NTD	Non-transfusion dependent
PD	Pharmacodynamic
PDGP	Protocol Deviation Guidance Plan
%	Percent
pH	Hydrogen ion concentration
PK	Pharmacokinetic
PPS	Per-Protocol Set
PRO	Patient-reported outcome
PROMIS	Patient-Reported Outcomes Measurement Information System
PT	Preferred term
PTT	Partial thromboplastin time
QD	Once daily
QoL	Quality of life
QT	Interval between Q and T waves
QTcF	Corrected interval between Q and T waves using Fridericia's correction formula
QUALMS	Quality of Life in Myelodysplasia Scale
RBC	Red blood cell
Rel Day	Relative study day
SAE	Serious adverse event
SAP	Statistical analysis plan
SCD	Sickle cell disease
SD	Standard deviation
SE	Standard error
SI	Système International
SOC	System organ class
SOE	Schedule of events
SRC	Safety Review Committee
TEAE	Treatment-Emergent Adverse Event
ULN	Upper limit of normal
WBC	White blood cell (count)

Abbreviation	Definition
WHO	World Health Organization

1. INTRODUCTION AND OBJECTIVES

1.1. Introduction

Due to the early termination of the current study, this statistical analysis plan (SAP) is created to support an abbreviated clinical study report (CSR), focusing on the primary and secondary endpoints, and the final safety update. Populations for analysis, data handling rules, statistical methods, and formats for data presentation are provided.

This SAP will also outline any differences between the current plan and the study protocol. Any revisions, updates, or differences will be documented and version controlled in the SAP and CSR.

1.1.1. Study Objectives and Endpoints

1.1.1.1. Primary

The primary objective of this study is to assess hematologic improvement based on an erythroid response (HI-E) for ≥ 8 weeks duration in patients with MDS within 24 weeks of etavopivat (FT-4202) treatment.

HI-E is defined based on transfusion history status at baseline, as defined in Section 1.2:

- Non-transfusion dependent (NTD): ≥ 1.5 g/dL increase in hemoglobin (Hb) from baseline maintained ≥ 8 consecutive weeks and no transfusion of RBC units for anemia over a continuous 8-week treatment period.
- Low transfusion burden (LTB): absence of any transfusion for ≥ 8 consecutive weeks.
- High transfusion burden (HTB): reduction by $\geq 50\%$ of red blood cell (RBC) units for ≥ 8 consecutive weeks.

1.1.1.2. Secondary

The secondary objectives are:

- 1) To assess the safety and tolerability of etavopivat in patients with MDS.
- 2) To assess additional measures demonstrating potential clinical benefit.

The secondary efficacy and safety endpoints are defined as the following:

- The incidence of adverse events (AEs), serious adverse events (SAEs), and AEs related to etavopivat.
- Number of premature discontinuations, dose interruptions, and dose reductions.
- Reduction in RBC transfusions and rate of RBC transfusion independence ≥ 8 weeks in patients with LTB or HTB at study entry.

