9.6.2.3 Additional Measures of Clinical Benefit

Additional measures of potential clinical benefit will be summarized with descriptive statistics. These consist of the following:

- Overall Response Rate (2006 IWG Criteria)
- Duration of response (2006 IWG Criteria)
- Increase in neutrophils and/or platelets
- Decrease in ferritin and decrease in iron chelation therapy
- Overall survival
- Reduction in RBC transfusions and rate of RBC transfusion independence (RBC-TI) in patients with LTB or HTB at study entry

The Overall Response Rate (ORR) and duration of response are based on the 2006 IWG Criteria (Cheson et al. 2006) as assessed at each scheduled assessment. ORR will be summarized with descriptive statistics by disease strata and overall. Duration of response will be summarized with quantiles based on product limit estimates (ie, Kaplan-Meier). Duration of response is defined as the time from date of first known incidence of a 2006 IWG criteria response to the most recent date that the 2006 IWG criteria is not met following the initial response. If the subject has met IWG criteria throughout the period following the initial response, the subject will be censored at the latest date of end of study, loss to follow-up, or death.

Overall survival is defined as the time from first dose to date of death. If the subject was alive at last contact, the end date will be censored at the latest of either end of study, loss to follow-up, or study discontinuation. Overall survival will be summarized with quantiles based on product limit estimates, in the same manner as the duration of response.

Laboratory results and change from baseline will be summarized with descriptive statistics for neutrophils and platelets. On-study use of iron chelation therapies will also be summarized with descriptive statistics. The study SAP will detail chelation therapy strata and summary methods as required.

For LTB and HTB patients, RBC transfusions will be summarized by both unit and volume with descriptive statistics by nominal visit. The incidence of 56-day transfusion independence by Week 16, Week 24, and Week 48 and duration of transfusion independence will be summarized with descriptive statistics.

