3.2. General Methods

In general, tables will summarize data by transfusion history stratum at Day 1. All statistical analyses will be performed using SAS statistical software Version 9.4 or higher, unless otherwise noted. For categorical variables, descriptive statistics will include frequency count and percentage. If missing is observed, a “Missing” category will be added without percentage. For shift tables, total rows and columns will not include patients from the “Missing” category except the “Missing” column and row and percentage will be calculated based on evaluable patients. For continuous variables, descriptive statistics are number of patients, mean, median, standard deviation (SD), 25th percentile (Q1), 75th percentile (Q3), minimum, and maximum.

For parameters assessed across multiple visits, by-visit summaries will be presented for planned visits from Table 1 and Table 2.

Minimum and maximum values will be presented to the same decimal precision as the raw values, mean, median, Q1, and Q3 values to one more decimal than the raw values, and the SD to two more decimals than the raw values. All percentages will be presented to one decimal place. All p-values will be presented with 4 decimal places and will be shown as ‘<0.0001’ if the value is smaller than 0.0001.

Relative study day will be provided in data listings. Day 1 is defined as the date of first treatment. Other study days are defined relative to Study Day 1. Relative day is calculated as (date of interest - date of the first treatment + 1) for study days on or after the date of the treatment start, and as (date of interest - date of the first treatment) for study days prior to the date of the treatment start.

Figures will be created to plot the data where it is deemed necessary. All data collected on study in the eCRF will be included in data listings.

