4.2.1. Analysis of Primary Endpoints

4.2.1.1. HI-E Response and MDS assessments

The proportion of patients with HI-E response ≥ 8 weeks within 24 weeks of etavopivat treatment will be analyzed across the pooled strata and within each stratum. Patients will be considered responders if they satisfy HI-E criteria during any continuous ≥ 8 -week treatment interval up to W24D1.

HI-E criteria are defined based on the patient's transfusion history stratum at D1:

NTD: A patient is considered a responder where at least one continuous interval ≥ 8 weeks occurs where all of the following criteria are met:

- Hb is increased by ≥ 1.5 g/dL relative to baseline at 2 or more consecutive visits
- Relapse date (date of first Hb measurement with < 1.5 g/dL change from baseline following the qualifying increase) occurs at least 8-weeks after the first incidence of qualifying Hb increase
- Patient is free of RBC transfusions

LTB: A patient is considered a responder if they are free of RBC transfusions over any continuous 8-week period.

HTB: A patient is considered a responder if they have a $\geq 50\%$ reduction in RBC transfusion burden relative to baseline RBC transfusion burden per 8 weeks over any continuous 8-week period.

Percent reduction in RBC transfusion burden is calculated for all rolling 56-day intervals in the 24-week primary treatment period (i.e. Days 2-57, Days 3-58,..., Days 113-168) as

$$-100 \times \frac{RBC \text{ units transfused in 56 day interval} - \text{Baseline RBC transfusion burden per 8 weeks}}{\text{Baseline RBC transfusion burden per 8 weeks}}$$

The numerator for the response rate will be the total number of responders (summed across all baseline transfusion categories). The denominator will be the number of patients in the EES.

MDS baseline assessment including the score based on Revised International Prognostic Scoring System (IPSS-R) for MDS and MDS response assessment will be presented in data listings.

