4.2.2. Analysis of Secondary Endpoints

4.2.2.1. Transfusion Burden

For the LTB and HTB strata only, the total RBC units transfused and % reduction from baseline will be summarized for each of the following 8-week study intervals: Week 1 to 8 (Rel Day 2 to 57), Week 9 to 16 (Rel Day 58 to 113), Week 17 to 24 (Rel Day 114 to 169), Week 25 to 32 (Rel Day 170 to 225), Week 33 to 40 (Rel Day 226 to 281), Week 41 to 48 (Rel Day 282 to 337).

% reduction from baseline in RBC transfusion burden is defined as

$$-100 \times \frac{\text{Total RBC Units Transfused During Interval}}{\text{Baseline RBC Units Transfused Per 8 Weeks}}$$

Patients who have discontinued treatment prior to completing the specified interval will be excluded from the analysis.

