5.2. Changes to Planned Analyses

For the purpose to support an abbreviated CSR, a selected set of endpoints are included in this SAP. The following analysis populations and endpoints mentioned in the protocol are not included:

Protocol Section 3.2:

- The HI-E for \geq 8 weeks within 16 and 48 weeks of etavopivat
- The HI-E for \geq 16 weeks within 24 and 48 weeks of etavopivat
- Overall response rate (2006 International Working Group [IWG] Criteria) (see protocol Appendix A)
- Duration of response (2006 IWG Criteria)
- Increase in neutrophils and/or platelets counts
- Decrease in ferritin and transferrin saturation (TSAT)
- Decrease in iron chelation therapy
- Overall survival

Protocol Section 3.3:

- PK: maximum observed plasma concentration, time to maximum observed plasma concentration, area under the plasma concentration-time curve from time zero until the last quantifiable time point (AUC0-last), from time zero to infinity (AUC0-inf), for a dosing interval (AUCtau/AUC0-24).
- RBC 2,3-DPG and ATP levels over time

Protocol Section 3.4:

- Change from baseline in Patient-Reported Outcome Measurement Information System (PROMIS) Fatigue Scale at Weeks 16, 24, and 48
- Change from baseline in The Quality of Life in Myelodysplasia Scale (QUALMS) patient-reported outcome assessment at Weeks 16, 24, and 48
- Cell colony analysis of bone marrow progenitors
- Cytomorphology (blast, M/E, and ringed sideroblast determination) and cytogenetics of bone marrow
- Markers of ineffective erythropoiesis and iron metabolism
- Cancer-associated mutations and/or genetic alterations in responding and non-responding patients
- Flow cytometry analysis of terminal erythroid differentiation

Protocol Section 9.2:

- Interim Assessment Set and Per-Protocol Set

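### The SAP keeps 8-week RBC transfusion independence as a secondary endpoint but plans no analysis of it, so the HTB rate is tabulated nowhere and the Week 16, Week 48 and duration summaries are missing for LTB and HTB alike

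*SAP*

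**What the plan says.** **The endpoint.** SAP 1.1.1.2 has three secondary bullets. Two concern safety and tolerability. The third, the only efficacy bullet, is "Reduction in RBC transfusions and rate of RBC transfusion independence" of at least 8 weeks in LTB or HTB patients. It matches the corresponding item in Protocol 3.2.

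**The protocol's analysis.** Protocol 9.6.2.3 plans a descriptive summary of "The incidence of 56-day transfusion independence by Week 16, Week 24, and Week 48", together with the duration of independence.

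**The SAP's analysis.** SAP 4.2.2 has a single subsection, 4.2.2.1: "For the LTB and HTB strata only, the total RBC units transfused and % reduction from baseline will be summarized" for six fixed 8-week intervals. Patients who stop treatment before an interval is complete are left out of that interval.

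**The primary endpoint by stratum (SAP 4.2.1.1).** For LTB: "A patient is considered a responder if they are free of RBC transfusions over any continuous 8-week period". For HTB, the requirement is at least a 50% "reduction in RBC transfusion burden relative to baseline RBC transfusion burden per 8 weeks over any continuous 8-week period". Results are given pooled and within each stratum, up to W24D1.

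**Declared omissions.** SAP 5.2 introduces its list with "The following analysis populations and endpoints mentioned in the protocol are not included". TI is not on that list. SAP 5.1 says that no endpoint clarifications are needed.

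**The concern.** The SAP supports an abbreviated report after early termination, so cutting secondary endpoints is legitimate, and SAP 5.2 does so openly for eight of the items in Protocol 3.2. TI was not cut. It stays in the endpoint list but has no definition, denominator, table or time limit in the analysis sections. A programmer who follows section 4 exactly would produce no TI result.

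The consequence is sharpest in HTB. There the planned output counts a patient who needed no blood for 8 weeks together with one whose units were halved. Appendix A of the protocol treats these as different levels of response, calling the first major and the second minor. Without a planned table, any HTB independence rate in the report would be an unplanned derivation, with its window rule and denominator chosen after the data are known.

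**Working it through.** The plan states no figure for this endpoint, so the check is to trace it through the documents and ask which planned output, if any, yields the rate.

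**Step 1. What each TI item in Protocol 9.6.2.3 has in the SAP.**

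| Item | LTB | HTB |
|---|---|---|
| TI by Week 24 | By-stratum HI-E result | None |
| TI by Week 16 | None | None |
| TI by Week 48 | None | None |
| Duration of TI | None | None |

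The HI-E analyses within 16 and 48 weeks, which might have supplied the LTB figures at those times, are themselves dropped in SAP 5.2.

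**Step 2. Why HI-E gives the LTB rate but not the HTB rate.** The LTB rule is zero RBC units over a continuous 8 weeks, which is TI itself. The HTB rule uses

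reduction = −100 × (units in 56-day interval − baseline units) / baseline units.

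Take a baseline of 4 units per 8 weeks:
- 0 units: −100 × (0 − 4)/4 = 100%. Responder, transfusion-independent.
- 1 unit: −100 × (1 − 4)/4 = 75%. Responder, not independent.
- 2 units: −100 × (2 − 4)/4 = 50%. Responder, not independent.

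All three add one to the same count. Provided the baseline is not zero, every independent HTB patient is an HI-E responder but not the reverse, so the HTB HI-E rate is only an upper bound for the HTB TI rate.

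**Step 3. How wide that leaves the answer.** This is an illustration under stated assumptions: 15 patients in each stratum as planned, and the 40% design response rate applying within each. Then 0.40 × 15 = 6 responders per stratum.
- HTB TI could be anything from 0/15 = 0% to 6/15 = 40%.
- Pooled LTB plus HTB TI could be anything from (6 + 0)/30 = 20% to (6 + 6)/30 = 40%.

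With fewer patients the lower bound for HTB is still zero.

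**Step 4. Whether the burden summary in SAP 4.2.2.1 recovers the count.** It does not.
- *Fixed against rolling windows.* Up to Week 24 the summary uses three intervals: Days 2–57, 58–113 and 114–169. The HI-E algorithm uses every 56-day window from Days 2–57 to Days 113–168, which is 113 − 2 + 1 = 112 windows. A patient transfused on Days 20, 90 and 150 is free of transfusion from Day 21 to Day 89, which is 89 − 21 + 1 = 69 days, and so qualifies as independent. All three fixed intervals nevertheless contain a transfusion.
- *Type of summary.* Mean, median, quartiles and range of units do not give the number of patients with zero units in at least one window.
- *The printed formula.* SAP 4.2.2.1 prints −100 × interval units / baseline units, without subtracting baseline. For 0 units this gives 0, where SAP 4.2.1.1 gives 100%. This is a separate inconsistency, but it means the percent-reduction column as printed would not show independence as a 100% reduction.

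**Step 5. Listings.** SAP 3.2 says "All data collected on study in the eCRF will be included in data listings". Protocol 8.2.2 collects the dates and units of transfusions. The data needed are therefore listed, but no derived TI status is specified.

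**The case against.** The best case for the plan is that little is lost. Transfusion dates and units are listed, and the percent reduction over every rolling window is already defined. An HTB patient with a 100% window is independent, so anyone can make the split. The reduction half of the secondary bullet is analysed, and the LTB rate to Week 24 is available. The summary is descriptive, with no test or decision attached, in a terminated single-arm study.

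Most of this stands, and it limits the point. A reader might infer that HTB independence is reported nowhere, or that HTB responders cannot be separated into independent and merely reduced. The documents do not support that: the information is in the listings, and only a planned, tabulated rate is missing. A reader might also infer that a whole secondary endpoint goes unreported. That too is more than the documents show, since only the TI part of a two-part bullet lacks an analysis, and for LTB at Week 24 even that is covered.

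The Appendix A distinction should be used with care. The trial's endpoints in Protocol section 3 do not use major and minor HTB response, so it shows why the split is informative, not that it was a planned level of analysis.

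What does not stand is the appeal to the abbreviated report. SAP 1.1 says that the report focuses on the primary and secondary endpoints and that differences from the protocol will be set out. SAP 5.2 sets them out, and TI is not among them. Hand derivation from listings does not replace an analysis that Protocol 9.6.2.3 specified.

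**Conclusion.** The point holds. A retained secondary endpoint has no analysis in the SAP. The HTB rate is tabulated nowhere, and the Week 16, Week 48 and duration summaries are missing for both strata. The LTB rate to Week 24 is the one part that can be read from planned output.

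The primary analysis is unaffected. The number of patients affected cannot be stated. It is tempting to say about 15 of 45, or 30 of 45 for LTB and HTB together, but those are planned enrolments. The study ended early, efficacy is analysed only in Week 24 completers with a baseline record, and neither document gives the actual counts. The ranges in the working rest on planned sizes and the design response rate, and show only that the HI-E result does not determine the HTB rate.

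The conclusion assumes that SAP section 4 is meant to be complete for the endpoints in SAP 1.1.1. If the omission was intended, the defect is instead a missing entry in SAP 5.2.

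**What to change.** Add SAP 4.2.2.2, Transfusion Independence:

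1. **Rate by Week 24.** Give n and % of LTB, HTB and pooled LTB plus HTB patients with at least one 56-day window of zero RBC units, using the rolling windows of SAP 4.2.1.1. An exact 95% confidence interval is optional, since Protocol 9.6.2.3 asks only for descriptive statistics.
2. **Population.** Use the EES, as SAP 4.2 specifies. Add a supportive version on the FAS that counts patients without such a window as non-independent, and label that counting rule as new. The SAP now uses a similar rule only in the informal futility assessment of 3.11.
3. **Weeks 16 and 48, and duration.** Add these from Protocol 9.6.2.3, or list in SAP 5.2, with the reason, any that will not be analysed. If Week 48 is kept, extend the windows past Day 168 and state the denominator for patients stopped by the termination. If duration is kept, define its start, end and censoring.

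While section 4.2.2 is open, reconcile the percent-reduction formula in 4.2.2.1 with that in 4.2.1.1.

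The cost is one short SAP section and one table. The Week 24 rate needs no new data and no new window definition, only a zero-unit condition on windows the SAP already defines. The documents do not say whether the code for those windows has been written.
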